7.2 PARTICIPANT DISCONTINUATION/WITHDRAWAL FROM THE STUDY

Providers

Providers may freely leave employment from HealthPartners. The timing of their employment will impact whether or not they are randomized, whether or not they receive training, whether or not they are exposed to the intervention, and whether or not they are lost to follow-up.

Patients

For the sub-sample of patients who are selected for a survey, patients are free to withdraw from participation in the survey at any time upon request. Patients may wish not to participate for any reason, including due to the perceived impact on their time or privacy. Within the parameters detailed in the MOP, study staff will provide support and encouragement to participants in order to minimize withdrawal and attrition for survey participation. Withdrawal from survey participation will be tracked by the CESR staff in the centralized study database.

7.3 LOST TO FOLLOW-UP

Providers

Providers are considered lost to follow-up if: they do not complete at least 6 extraction encounters in the intervention period. Providers lost to follow-up are not replaced and would be excluded from the analysis.

Patients

Patients are considered lost to follow-up if they meet any of the following criteria: (1) they withdraw from participation in the survey at contact or after completing any portion of the survey; (2) they cannot be reached after all call attempts have been made; (3) they cannot be reached within the defined survey window. Such patients would be excluded from the analysis for survey related objectives. It is anticipated that patients will be lost to follow-up by the nature of survey data collection and sample size selection is made with attention to the anticipated size of this group. If more patients are lost to follow-up than anticipated, additional patients will be sampled.

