5 STUDY POPULATION

5.1 INCLUSION CRITERIA

Providers

In order to be eligible to participate in this study, an individual must meet all of the following criteria:

- Have a current Drug Enforcement Administration (DEA) number allowing them to write prescriptions for controlled substances, including opioids, during the baseline period
- Perform dental extractions of permanent teeth on a regular basis (a minimum of 6 extraction encounters during the baseline period)

Patients

In order to be eligible to participate in this study, an individual must meet all of the following criteria:

- Have a dental extraction of a permanent teeth performed by an eligible HealthPartners provider during the intervention period

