6.3 MEASURES TO MINIMIZE BIAS: RANDOMIZATION AND BLINDING

The randomization of providers to study arm will utilize stratification on baseline factors in order to balance key provider factors evenly across study arms. Specific stratification factors to be utilized will be outlined in the Statistical Analysis Plan. Providers will be randomly allocated 1:1:1 through a computer-generated program to either Standard Practice, CDS, or CDS-E. Patients will be exposed to the intervention to which their provider has been randomized based on the provider they see at the index extraction visit. Systematic sampling with a variable sampling ratio by provider will be used to identify a sample of patients to receive the post-visit survey. This sampling strategy will approximate stratified random sampling and ensure roughly equal counts of patient surveys by provider and study arm. At each patient encounter, the CDS Web service will collect patient level data from the EHR (e.g., medical conditions, current medications, social history). Providers assigned to the CDS or CDS-E arms will be able to access the information using the CDS tool. Providers assigned to the control arm will continue to use their usual methods to assess and address pain management for dental procedures without any effort to influence their prescribing of analgesics following the dental extraction. They will not be shielded from other outside influences.

At the index encounter (the initial patient visit for a dental extraction during the intervention period where all the study criteria are met), the patient is assigned a unique study identifier that is used to link patient encounter data over time. All index and subsequent encounter data for eligible patients are stored in a limited de-identified analysis dataset.

In order to minimize contamination across study arms, only providers in the CDS or CDS-E arms will be able to access the clinical decision support. Similarly, patients who receive care from providers in the CDS-E arm will have access to supplemental patient education. As such, both groups will know their assignment. The study team will not disclose the study's purpose, objectives, or outcomes measures directly to patients until after the encounter or after the participant has been surveyed about their experience, if selected.

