9.3 POPULATIONS FOR ANALYSES

Patient Encounter Study Population for H1, H2

The analytic denominator for H1 and H2 will consist of up to 16,800 (8400 baseline and 8400 intervention) first extraction encounters of patients aged 16 and higher and linked to a study-eligible provider, and who have a permanent tooth extraction during the year prior or year after the implementation of the strategies.

Patient Study Population for H3, H4

The analytic denominator for H3 and H4 will start with the approximately 8,400 patients who meet the criteria for the analytic denominator during the intervention period for H1 and H2 above. This analytic dataset will be further reduced to the approximately 1,520 patients who are approached to complete and complete a patient survey within 6 days of the index encounter. Of the approximately 1,520 patients approached it is expected that the analysis for H3 and H4 will include data from 1,200 patients.

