9.4.2 ANALYSIS OF THE PRIMARY EFFICACY ENDPOINT(S)

H1: Providers in the CDS and CDS-E strategy arms will reduce their likelihood of prescribing opioids for patients following extractions more than providers in the SP arm.

Analysis plan: Hypothesis H1a posits that patient encounters at which extractions are performed by dental providers in the CDS and CDS-E arms will have a larger reduction in the likelihood of receiving an opioid prescription at the index encounter than patient encounters in the SP arm when comparing independent samples of patient encounters before the implementation to patient encounters following the implementation. A generalized linear mixed-model regression with a logit link and binomial error distribution will be used to test the effects of the implementation strategies. The patient-level endpoint (patient received an opioid prescription at the index encounter) is coded as a binary outcome variable. This endpoint will be predicted by 2 fixed-effects terms for study arm of CDS (CDS vs. SP) and CDS-E (CDS-E vs. SP), year in which the patient has an extraction (post or pre-implementation), and by interaction terms of study arm and year. A random intercept for provider will be included in the model to accommodate the cluster-randomized design with providers as the unit randomized. Additional covariates to be included will be described in the MOP. Model-predicted proportions and confidence intervals of opioid prescribing will be summarized by time and study arm jointly. Contrasts will estimate differential reduction in the endpoint comparing CDS vs. SP and CDS-e vs. SP. This analysis will be conducted on the Intention to Treat Analysis Dataset.

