9.4.3 ANALYSIS OF THE SECONDARY ENDPOINT(S)

H2: Providers in the CDS and CDS-E strategy arms will increase their likelihood of satisfying the composite endpoint defined by: 1) prescribing or recommending non-opioid analgesics at the extraction encounter and 2) not prescribing opioids at the index encounter for patients following extractions more than providers in the SP arm.

Analysis plan: Hypothesis H2 posits that patient encounters at which extractions are performed by dental providers in the CDS and CDS-E arms will have a larger increase in the likelihood of receiving a prescription or recommendation for non-opioid analgesics and not prescribing opioids at the index encounter than patient encounters in the SP arm when comparing independent samples of patient encounters before the implementation to patient encounters following the implementation. The same analytic strategy used for the primary endpoint will be used for this secondary endpoint and will be conducted on the Intention to Treat Analysis Dataset.

H3 (alternative): Patients will report higher levels of the extent of shared decision making in the CDS-E arm than the CDS or SP arms.

Analysis plan: Hypothesis H3 posits that patients will report higher levels of the extent of shared decision making in the CDS-e arm than CDS or SP arms during the strategies implementation time period. A general linear mixed-model regression with an identity link and normal error distribution will be used to test the effects of the implementation strategies. The patient-level endpoint is the score on the 3-item composite of adapted Collaborate Shared Decision Making, and is considered an interval-level variable. This endpoint will be predicted by 2 fixed-effects terms for study arm of CDS (CDS vs. SP) and CDS-E (CDS-E vs. SP). A random intercept for provider will be included in the model. Additional covariates to be included will be described in the MOP. Model-predicted means and confidence intervals for the endpoint will be summarized by study arm. A contrast will estimate the difference in the mean of the endpoint for patients in the CDS-e arm vs. CDS and SP (pooled). This analysis will be conducted on the Intention to Treat Analysis Dataset.

H4 (descriptive): Compare patient report of mean pain in the week following tooth extraction across the 3 study arms.

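### Section 7.3 drops randomised providers with fewer than 6 intervention-period extraction encounters, which contradicts the intention-to-treat analysis of H1 and H2 and the population in section 9.3

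*Combined protocol and SAP*

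**What the plan says.** Section 7.3 treats providers as lost to follow-up if "they do not complete at least 6 extraction encounters in the intervention period". The consequence follows: "Providers lost to follow-up are not replaced and would be excluded from the analysis". The same section also excludes patients, but limits that to the survey: "Such patients would be excluded from the analysis for survey related objectives". The provider sentence has no such limit.

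The statistical sections describe a different set:

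- Section 9.4.2, for H1: "This analysis will be conducted on the Intention to Treat Analysis Dataset".
- Section 9.4.3, for H2: the strategy of the primary analysis "will be used for this secondary endpoint and will be conducted on the Intention to Treat Analysis Dataset".
- Section 9.3, for both: "first extraction encounters of patients aged 16 and higher and linked to a study-eligible provider", with a permanent tooth extraction in the year before or after implementation. No minimum intervention-period count is given.
- Section 5.1, on provider eligibility: a DEA number and "a minimum of 6 extraction encounters during the baseline period". Both conditions refer to the baseline period.

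The Intention to Treat Analysis Dataset is named but not defined in the available text. The only sensitivity analyses specified (section 9.4.5) concern patient covariates.

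**The concern.** In a trial that randomises providers, intention to treat means that every randomised provider is analysed in the assigned arm. A rule that removes providers for low volume after allocation breaks this, even when it is written in advance and applied alike in all arms. The plan claims the property in sections 9.4.2 and 9.4.3 and gives it up in section 7.3.

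Two things are at stake. First, two analysts who follow this plan could analyse different sets of clusters, and the choice could be made after the data are seen. Second, the exclusion could be related to arm. Section 6.3 says of the CDS and CDS-E providers and the CDS-E patients: "As such, both groups will know their assignment". Section 7.2 lets providers leave employment and ties the timing of employment to loss to follow-up. Arm-related loss therefore cannot be ruled out, although the documents do not show that it occurs.

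**Working it through.** **1. The passages side by side.** Take a randomised provider, eligible at baseline, by number of intervention-period encounters:

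| Intervention encounters | Under 9.3 with 5.1 | Under 7.3 |
|---|---|---|
| 6 or more | baseline and intervention encounters in | in |
| 1 to 5 | baseline and intervention encounters in | all out |
| 0 | baseline encounters in; no post-period outcome exists | all out |

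The last two rows conflict. Section 4.4 adds a further tension: a provider who leaves employment counts there as having completed the study, while 7.2 and 7.3 can make the same provider lost to follow-up and excluded.

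**2. The plan's own power figure.** Section 9.2 gives 51 providers, 6,900 patients per period, ICC 0.3, two-sided alpha 0.05, and post-implementation rates of 15% against 38%, with 80% power.

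- Encounters per provider per period: 6,900/51 = 135.3. Providers per arm: 51/3 = 17.
- Design effect: 1 + (135.3 − 1) × 0.3 = 41.29.
- Effective n per arm: 17 × 135.3/41.29 = 55.7.
- Power of a two-proportion comparison of post-period rates: 0.794 (0.789 to 0.813 across variants of the test).

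The 80% reproduces with all 51 providers contributing, so the sample size makes no allowance for excluded providers.

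**3. What a low-volume provider contributes.** With a random intercept for provider, as planned, and m0 baseline and m1 intervention encounters, a provider's within-provider information on pre-post change is proportional to m0·m1/(m0 + m1).

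- Typical provider: 135 × 135/270 = 67.5.
- Provider with 5 intervention encounters: 135 × 5/140 = 4.82.
- Ratio: 4.82/67.5 = 0.071, about 7%.

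A linear mixed model with ICC 0.3 (a linear approximation to the logit model) gives ratios of 0.077 with 5 intervention encounters, 0.022 with 1 and 0.007 with none.

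**4. Effect of dropping rather than keeping.** Assumptions, none from the documents: 3 of 17 providers in one arm have 135 baseline and 5 intervention encounters; their change differs by 20 points from that of the other 14; all other providers, including the 17 in the comparator arm, have 135 and 135.

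- Weight of the three if kept: 3 × 0.0714/(14 + 3 × 0.0714) = 0.2143/14.2143 = 0.0151.
- Shift in the arm's estimated change: 0.0151 × 20 = 0.30 points.
- Contrast variance if dropped: 1/14 + 1/17 = 0.1303. If kept: 1/14.2143 + 1/17 = 0.1292. SE ratio: √(0.1303/0.1292) = 1.004.

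The full linear mixed model gives 0.30 points and an SE ratio of 1.0045.

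**5. Dependence on the model.** If the model also had a provider-by-period effect, which the plan does not specify, low-volume providers would carry more relative weight. The same case then gives:

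| Between-period correlation (assumed) | Shift, points | SE increase from dropping |
|---|---|---|
| 1 (planned model) | 0.30 | 0.45% |
| 0.9 | 1.32 | about 2.0% |
| 0.5 | 2.39 | 3.9% |

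The documents give no value for this correlation.

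**The case against.** The strongest reply is that the rule hardly matters. The illustration is a severe one: the assumed 20-point difference is close to the whole 23-point effect in section 9.2, yet the estimate moves by 0.3 points in the planned model. The larger shifts belong to a model the plan does not use. This stands, and those figures should be read only as a guide to model dependence.

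Nor should lost power be charged to the rule. In the same case, and relative to an arm with full volume, the contrast SE rises by about 5.2% if the three providers are dropped and still by about 4.7% if they are kept. Low volume causes the loss, not section 7.3. This also stands.

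The rule is prespecified, identical across arms, mirrors the baseline threshold, and depends on volume rather than on outcome or use of the CDS. Section 7.2 names no arm-related cause of loss. That makes bias less likely, but volume and employment are still observed after allocation.

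Section 7.3 could be read as a specific exclusion that qualifies the general denominator in 9.3. Nothing says so, and on that reading the intention-to-treat label would be wrong.

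The definition might sit in a separate document: section 6.3 points to a Statistical Analysis Plan for the stratification factors, and section 9.4 points to the Manual of Procedures for covariates. The absence of a definition can be stated only for the text at hand. The conflict within that text remains either way.

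**Conclusion.** The concern holds. Section 7.3 as written excludes randomised clusters on a post-allocation count, without limiting the exclusion to any one analysis, and this cannot be squared with the intention-to-treat analyses of H1 and H2 or with the population in 9.3. The conclusion rests on the wording and needs no calculation.

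The numerical consequence is probably small: about 0.3 points on one arm's change under the assumptions shown, in the planned random-intercept model and a linear approximation. The number of providers affected and the direction of any bias cannot be derived from the documents. The matter should be fixed because it leaves the primary analysis population unsettled and departs from intention to treat without need, not because a large bias has been shown.

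**What to change.** - **Section 7.3:** delete the clause that excludes lost-to-follow-up providers from the analysis. The statement that they are not replaced can stay.
- **Section 9.3:** define the Intention to Treat Analysis Dataset as all eligible baseline and intervention encounters of every randomised provider, analysed in the assigned arm whatever the intervention-period volume. Providers with no intervention encounters then contribute baseline data only.
- **Reporting:** give the number of low-volume and departed providers by arm.
- **Sensitivity analysis:** keep the restriction to 6 or more intervention encounters only as a labelled sensitivity analysis of H1 and H2.

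An explicitly defined modified intention-to-treat set, with exclusions reported by arm, would also remove the ambiguity. It would keep the post-allocation selection, however, and retaining the providers costs nothing extra.

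The cost is a short amendment to 7.3 and 9.3. No new data are needed, because the encounters are already in the health-record extract.

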5.5 STRATEGIES FOR RECRUITMENT AND RETENTION

Implementation of the CDS is considered a HealthPartners Dental Group initiative. The project is being implemented with the aim of reducing opioid prescribing. Consent has been provided by dental leadership in accordance with HealthPartners practices.

Providers randomized to the CDS or CDS-E will be exposed to the clinical decision support, integrated into the EHR. Patients who receive care from providers randomized to the CDS-E arm will also be exposed to study-specific patient education.

For the subset of patients eligible to receive a survey, patients will provide verbal consent for survey participation via telephone, which will be obtained by trained survey administrators. If a patient chooses not to participate, another patient will be sampled and called.

Further information about the strategies for recruitment and retention are detailed in the Manual of Procedures.

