H3 endpoint: Mean of the 3-item composite of adapted Collaborate Shared Decision Making score reported by the patient within 3-6 days of the extraction encounter.

Sample size: Survey materials will be sent to 1520 patients. The historical response rate for dental research surveys at the organization is 79%, yielding surveys returns from 1200 patients.

H4 (descriptive): Compare patient report of average pain in the week following extraction across the 3 study arms.

H4 endpoint: Mean pain rating in the 3-6 days since the extraction encounter, self-reported by patients within 3-6 days of the extraction encounter.

Samples size: This analysis will use the same analytic sample from the patient survey as described in H3.

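### Section 7.3 drops patients who withdraw part-way through the survey from H3 and H4, even when the endpoint answer is already recorded; the likely effect is small and the remedy cheap

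*Combined protocol and SAP*

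**What the plan says.** Section 7.3 gives three ways for a survey patient to be lost to follow-up. The first is that "they withdraw from participation in the survey at contact or after completing any portion of the survey"; the other two cover patients who could not be reached at all or not within the survey window. All three have the same consequence: "Such patients would be excluded from the analysis for survey related objectives". The survey objectives are H3 and H4.

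The analysis sections do not soften this:

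- Section 9.3 limits the H3 and H4 population to patients who complete a survey within 6 days of the index encounter.
- Section 9.4.3 does the same for H4.
- For H3, section 9.4.3 says that "The patient-level endpoint is the score on the 3-item composite of adapted Collaborate Shared Decision Making". It assigns the analysis to the Intention to Treat Analysis Dataset, which the documents do not define, and gives no rule for a partly answered survey.

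Multiple imputation and missing-at-random appear only in the abbreviation list (section 10.3). No missing-data method is described for the survey endpoints.

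On withdrawal itself, section 7.2 says that "patients are free to withdraw from participation in the survey at any time upon request". It does not say what happens to answers already given.

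Shortfalls are made up by more sampling. Section 5.5 states "If a patient chooses not to participate, another patient will be sampled and called", and section 7.3 adds "If more patients are lost to follow-up than anticipated, additional patients will be sampled".

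**The concern.** H3 needs three items and H4 needs one pain rating. A patient can supply either and then stop. Under section 7.3 that patient is handled like someone who was never reached, and is removed from both analyses although at least one endpoint is fully observed.

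The trigger occurs at the survey call, which the Schedule of Activities places at Day 4 (-1/+2 days), after the extraction and after any exposure to the intervention. Selecting patients on such an event can distort an arm comparison if stopping is related to the outcome and differs by arm. Section 2.3.1 accepts that a shift in prescribing could leave pain under-controlled, and H4 is the patient-reported pain endpoint that would show it. Sampling replacements restores the count but does not undo the selection.

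**Working it through.** **1. The plan's own figure.** Section 9.2 states "Survey materials will be sent to 1520 patients" and then "The historical response rate for dental research surveys at the organization is 79%, yielding surveys returns from 1200 patients". The check is 1,520 × 0.79 = 1,200.8, which agrees with 1,200. In reverse, 1,200 / (1 − 0.21) ≈ 1,519. The documents give no SD, effect size, ICC or power for H3 or H4, so there is no power figure to reproduce.

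**2. Where the excluded patients sit.** Section 9.3 expects 1,200 patients in the H3 and H4 analyses. Anyone removed under section 7.3 is outside that number, among 1,520 − 1,200 = 320 patients (320 / 1,520 = 21.1%). The documents do not say how many of the 320 would be part-way withdrawals.

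**3. Which criterion discards data.** Refusal at contact and failure to reach the patient leave nothing to analyse. Only the part of the first criterion about withdrawing after some of the survey can discard an observed endpoint. Even then, whether the H3 items or the pain rating had been reached depends on the item order, which is not given.

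**4. Precision (assumed inputs).** Let q be the share of patients with a recorded endpoint who withdrew part-way, in addition to 1,200 completers. Patients recovered = 1,200 × q / (1 − q). The standard error falls by the factor √(1 − q), ignoring clustering.

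| q | Patients recovered | As a share of 320 | Fall in SE |
|---|---|---|---|
| 1% | 12 | 3.8% | 0.5% |
| 2% | 24 | 7.5% | 1.0% |
| 5% | 63 | 19.7% | 2.5% |
| 10% | 133 | 41.6% | 5.1% |

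The last row needs about two fifths of all planned non-response to be part-way withdrawals with a usable endpoint, so it is an extreme case.

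**5. Bias (assumed inputs).** Suppose the excluded patients in an arm differ from that arm's completers by g SD. The completers' mean then misses the mean of all patients with recorded data by q × g. If g is the same in arms A and B, the contrast shifts by (qA − qB) × g.

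- 5% against 2%, g = 0.25: 0.03 × 0.25 = 0.0075 SD
- 5% against 2%, g = 0.5: 0.03 × 0.5 = 0.015 SD
- 10% against 5%, g = 0.25: 0.05 × 0.25 = 0.0125 SD
- 10% against 5%, g = 0.5: 0.05 × 0.5 = 0.025 SD
- Equal shares and the same g: 0

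Equal shares alone do not guarantee zero. With 5% in both arms and g of 0.5 and 0.25, the shift is 0.05 × 0.5 − 0.05 × 0.25 = 0.0125 SD.

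**6. Scale.** The H3 contrast in section 9.4.3 is CDS-E against CDS and SP pooled, taken here as 400 against 800. At two-sided 0.05 and 80% power, the detectable difference is (1.960 + 0.842) × √(1/400 + 1/800) = 0.17 SD with no clustering. With 1,200 / 51 = 23.5 surveys per provider and an assumed ICC of 0.10, the design effect is 1 + 22.5 × 0.10 = 3.25. The detectable difference is then 0.17 × √3.25 ≈ 0.31 SD. The shifts in step 5 are well below either value.

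**The case against.** The strongest reply is that section 7.3 speaks of withdrawing from participation. Sections 7.2 and 10.1.1.2 treat withdrawal as a consent right exercised on request, and section 7.2 gives privacy as one possible reason. On that reading, setting aside a withdrawn patient's answers is a cautious choice, and a call that is simply cut short may not be covered at all. This stands in part. The documents neither require deletion nor state that answers may be kept, and the verbal consent script that could settle it is not among them. It supports separating the two situations. It does not support leaving them merged.

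It is also fair to say that the endpoints are secondary (H3) and descriptive (H4), that the primary endpoint and H2 come from the health record and are untouched, and that the general 21% non-response is a larger possible source of selection, which this change does not address. All of that stands, and it limits the importance of the point.

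A reader might infer more than the documents support:

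- **That a few percent of the 1,200 respondents are being lost.** The 1,200 are the patients expected in the analysis. The excluded patients are among the other 320, and their number is not given.
- **That pain will look milder in one particular arm.** No passage links stopping early to pain, dissatisfaction or arm, so the direction is unknown.
- **That usable data are certain to be lost.** Without the item order, the group who stop after giving an endpoint could be very small or empty.

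**Conclusion.** The point holds as a minor one. Section 7.3 states a rule, the completer restrictions in sections 9.3 and 9.4.3 point the same way, and no passage keeps an H3 composite or pain rating that is already recorded. The rule therefore selects, avoidably, on a post-intervention event.

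The size cannot be computed from the documents. If 2% to 10% of patients with a recorded endpoint withdraw part-way, with a gap of 3 to 5 percentage points between arms and an outcome difference of 0.25 to 0.5 SD, the contrast shifts by about 0.01 to 0.03 SD. It does not shift if shares and differences match across arms. These inputs are assumptions, and the calculation covers only the part-way withdrawals. A conclusion that H3 or H4 is materially biased would not be supported. The case for acting is that the rule discards observed outcomes for no stated reason, and that settling it before analysis avoids a later choice made with the data in view.

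**What to change.** - **Section 7.3:** distinguish stopping the survey early from asking for answers to be removed. Exclude only patients with no recorded endpoint item and those who ask for removal. Check that this agrees with the consent script.
- **Section 9.3:** define the H3 set as all sampled patients with a scorable three-item composite, and the H4 set as all with a recorded pain rating, whether or not the rest of the survey was finished. State what makes the composite scorable.
- **Section 9.4.3:** use the same two sets, in place of the undefined dataset for H3 and the completer subset for H4. Changing section 7.3 alone would leave the other sections contradicting it.
- **Reporting:** give the number of partial surveys by arm, and repeat H3 and H4 on completers only as a sensitivity analysis.

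The cost is a few sentences across three sections. Survey answers are already entered in REDCap (section 8.1) and survey withdrawals are already tracked (section 7.2), so no new outcome data are needed; the tracking record need only show whether removal was requested. The one downside is that H3 and H4 will have slightly different denominators.
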